Protocol Summary

Study Acronym/Protocol #: AAA 13-02

06 Dec 2017

NCT02528500

CONFIDENTIAL INFORMATION

PROTOCOL SUMMARY

Study Title	Early Feasibility Assessment of the GORE® EXCLUDER® Thoracoabdominal Branch Endoprosthesis in the Treatment of Type IV Thoracoabdominal Aortic Aneurysms Involving the Visceral Branch Vessels
Protocol Number	AAA 13-02
Sponsor	W. L. Gore & Associates, Inc. Medical Products Division [contact]
Study Design	This is a non-randomized, multicenter study designed to assess the initial feasibility of the GORE® EXCLUDER® Thoracoabdominal Branch Endoprosthesis (TAMBE Device)
Study Objective	Assess the initial safety of the TAMBE Device implantation procedure in the treatment of Aortic Aneurysms Involving the Visceral Branch Vessels
Study Rationale	This study is designed to provide evidence to support the use of the TAMBE Device as an option for endovascular treatment of patients with Type IV Thoracoabdominal Aortic Aneurysms.
Study Endpoints	
Primary endpoint:
 
Procedural Safety - Absence of the following events through 30 days post-procedure:
 
 • Death • Stroke • Myocardial Infarction • Bowel Ischemia • Paraplegia • Respiratory Failure • Renal Failure • Procedural Blood Loss ≥1000 mL 
Secondary endpoints:
 
Technical Success - All of the following:
 
 • Successful access to the necessary arterial sites • Successful deployment of all required TAMBE Device components and any required accessory components • Patency of all required TAMBE Device components and any required accessory components on completion angiography • Absence of surgical conversion within 24 hours of initiation of the procedure

	
Device integrity - Absence of the following events through one year of follow-up:
 
 • Loss of functional patency in any branch component due to thrombus or mechanical failure of the branch components • Loss of functional patency in the main body component(s) due to thrombus or mechanical failure of the main body component(s) • Separation of the branch components from the main body component(s) • Separation of the main body component(s) from the accessory components (Distal Bifurcated Component and / or contralateral limb components) 
Individual components of technical success Individual components of device integrity at one month, six months and one year follow-up Patency (Primary, Assisted Primary and Secondary) Absence of Type I and Type III endoleaks at one month follow-up

Subject Population	Subjects with Thoracoabdominal Aortic Aneurysms Involving the Visceral Branch Vessels
Number of Subjects Treated	10
Number of Sites	Six in the United States
Expected Time to Complete Enrollment	18 Months
Schedule of Events	
Assessments at Pre-treatment:
 
 • CT of chest, abdomen and pelvis • Physical exam • Creatinine measurement 
Assessments at Treatment:
 
 • Angiography 
Assessments at Hospital Discharge:
 
 • Physical exam • Creatinine measurement • Abdominal ultrasound (optional) 
Assessments at Follow-up (One month, six months, and annually through 5 years):
 
 • CT of chest, abdomen and pelvis (not required at hospital discharge) • Lumbar spine series X-ray (4 views) (annual follow-up only)* • Physical exam • Creatinine measurement • Abdominal ultrasound (optional) 
*As enrollment is closed for this study, for all subjects that have completed their one year follow-up prior to this protocol amendment being implemented, subjects will be

CONFIDENTIAL INFORMATION

	expected to have radiograph assessments at their next annual follow-up exam (i.e. two year follow-up) and annually thereafter.
Anticipated Total Study Duration	7 years from initiation of enrollment

**CONFIDENTIAL INFORMATION**

## 1.0 Introduction

This Statistical Analysis Plan (SAP) describes the statistical analyses planned to address the objectives of the GORE® EXCLUDER® Thoracoabdominal Branch Endoprosthesis study (AAA 13-02). This SAP summarizes the analyses that will be performed for the initial assessment of the feasibility of the GORE® EXCLUDER® Thoracoabdominal Branch Endoprosthesis (TAMBE Device) for treatment of aortic aneurysms involving the visceral branch vessels. This SAP outlines tables, figures, and listings that are included in reports for the AAA 13-02 clinical study.

## 2.0 Study Design Overview

### 2.1 Primary Objective

The primary objective of the GORE® EXCLUDER Thoracoabdominal Branch Endoprosthesis study (AAA 13-02) is to provide an initial assessment of the feasibility of the TAMBE Device in the treatment of aortic aneurysms involving the visceral branch vessels.

### 2.2 Design Summary

The AAA 13-02 study will be a prospective, nonrandomized, multicenter, single-arm evaluation designed to provide an initial assessment of the feasibility of the TAMBE Device in the treatment of aortic aneurysms involving the visceral branch vessels. Six sites in the United States and one site in Brazil, and an estimated maximum of 20 subjects treated with the TAMBE Device will participate in this study. Subjects may be enrolled into the clinical study provided all inclusion/exclusion criteria are met. Subjects will be evaluated through hospital discharge and return for follow-up visits at one (1), six (6), 12, 24, 36, 48 and 60 months. Subject accrual is anticipated to be 18 months.

### 2.3 Study Endpoints

#### 2.3.1 Primary Endpoint

The primary endpoint of the study will be procedural safety defined as the absence of the following events through 30 days post-procedure:

- Death
- Stroke
- Myocardial Infarction
- Bowel Ischemia
- Paraplegia
- Respiratory Failure
- Renal Failure
- Procedural Blood Loss  $\geq 1000$  mL

These events will be adjudicated to the definitions provided in Appendix A of the protocol by a CEC.

**CONFIDENTIAL INFORMATION**

### 2.3.2 Secondary Endpoints

Secondary endpoints include the following:

- Technical Success, including individual components of technical success
- Device Integrity, including Individual components of device integrity
- Patency (Primary, Assisted Primary, and Secondary)
- Absence of Type I and Type III endoleaks at one month follow-up

Technical success is defined as:

- Successful access to the necessary arterial sites
- Successful deployment of all required TAMBE Device components and any required accessory components
- Patency of all required TAMBE Device components and any required accessory components on completion angiography
- Absence of surgical conversion within 24 hours of initiation of the procedure

Device integrity will be defined as freedom from all of the following events in the first year of follow-up.

- Loss of functional patency in any treated branch component due to thrombus or mechanical failure of the branch component
- Loss of functional patency in the main body component(s) due to thrombus or mechanical failure of the main body component(s)
- Separation of the treated branch components from the main body component(s)
- Separation of the main body component(s) from the accessory components (Distal Bifurcated Component Device and / or Contralateral Leg Components)

The definitions for device integrity in Appendix A of the protocol were based on the proposal outlined in Chaikof et al.[1]. These events will be adjudicated by a CEC. Device integrity and its individual components will be reported at interim follow-up time points as well, including one and six months.

Patency will be assessed using Kaplan-Meier analysis. Subjects not experiencing an event will be censored at time of last follow-up or contact. Subjects having events are defined below:

- Primary patency - Blood flow without occlusion maintained through the device after implant without an intervention. Subjects who have a reintervention on a treated segment before occlusion to prevent eventual loss of patency, after occlusion to restore patency, or open surgical bypass to restore patency will have lost primary patency at the earliest such reintervention.

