## 5.0 Statistical Analyses

### 5.1 Analysis Populations

All enrolled Subjects will be included in reported data.

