**CONFIDENTIAL INFORMATION**

when enrollment is complete and available Subjects have completed 12-month follow-up assessment. Serial analyses of long-term results will occur during the follow-up period. No adjustment to overall alpha level will be made since this is an exploratory study designed to evaluate basic feasibility.

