### 5.3 Statistical Analysis of Endpoints

Due to the exploratory nature of this study, statistical analysis will be limited to summary statistics, including frequency counts for categorical variables, and measures of dispersion for continuous variables. No inferential analysis will be performed.

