#### 5.4.2 Core Laboratory

An independent Core Laboratory (Core Lab) will provide review of imaging data collected during the study at pre-treatment and follow-up.

Summaries of qualitative Core Lab imaging findings (endoleak, wire fracture, component separation, patency, and rupture) will be provided at each analysis window. The denominator for each category will be the number of subjects with a CT imaging assessment in the given window which is read by the Core Lab.

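### Read literally, the SAP counts a subject lost or not imaged before 12 months, with no reported event, as free of device-integrity events for the whole year

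*SAP*

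**What the plan says.** - **Endpoint.** SAP 2.3.2: "Device integrity will be defined as freedom from all of the following events in the first year of follow-up". The Protocol Summary (Study Endpoints) agrees: "Absence of the following events through one year of follow-up". Four events are listed: loss of flow in a branch, loss of flow in the main body, and two kinds of component separation. Death, withdrawal and missed imaging are not among them. SAP 2.3.2 also asks for the composite and its components at one and six months.
- **Population.** SAP 5.1, in full: "All enrolled Subjects will be included in reported data".
- **Method.** SAP 5.3: "statistical analysis will be limited to summary statistics, including frequency counts for categorical variables".
- **How events are found.** Under SAP 4.4 the CEC adjudicates adverse events that have been reported. With no report there is no event.
- **Timing.** Under SAP 5.2 the final endpoint analysis takes place "when enrollment is complete and available Subjects have completed 12-month follow-up assessment". Incomplete follow-up is foreseen, but nothing is said about subjects who are not available.
- **Rules for incomplete follow-up in other analyses.** For patency, SAP 2.3.2 says "Patency will be assessed using Kaplan-Meier analysis" and "Subjects not experiencing an event will be censored at time of last follow-up or contact". For Core Lab imaging findings, SAP 5.4.2 says: "The denominator for each category will be the number of subjects with a CT imaging assessment in the given window". Neither rule is extended to device integrity.

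**The concern.** A one-year freedom-from-event rate needs a rule for subjects not observed for a year. The SAP has such a rule for two overlapping analyses and none for this one. Loss of flow is censored in the patency analysis but uncensored as a device-integrity component. Component separation has an imaged-subject denominator as a Core Lab finding but none as a device-integrity component. One report could therefore show different rates for overlapping device failures, with nothing to reconcile them.

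A programmer who applies the stated population and method will put a subject lost at month 2 in both numerator and denominator of the 12-month rate. No test is planned, so the reported proportion is itself the result. With 10 to 20 subjects, the choice of denominator is visible in it, and an unwritten denominator can be chosen after the data are seen.

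**Working it through.** The documents give no expected device-integrity rate, event rate or dropout rate, so there is no planned figure to reproduce. Every e and d below is an assumption. N is 10 (Protocol Summary) or 20 (the maximum in SAP 2.2); that the two differ is a separate matter.

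**Formulas.** Let e be the subjects with an event and d the event-free subjects without 12-month status.
- Crude, the literal reading: (N − e)/N. It does not depend on d.
- Assessed-only (an event, or known 12-month status): (N − d − e)/(N − d).
- Missing counted as failure, an extreme lower bound: (N − d − e)/N.
- Kaplan-Meier lies between assessed-only (all d leave before the first event) and crude (all d leave after the last event).

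**Example 1.** N = 10, events at days 180 and 365, losses at days 60, 90 and 200.
- Crude: 8/10 = 80%.
- Kaplan-Meier: 8 at risk at day 180 and 6 at day 365, so (7/8) × (5/6) = 0.729, about 73%.
- Assessed-only: 5/7 = 71%.

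**Example 2.** N = 20, e = 2.

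| d | Crude | Assessed-only | Missing as failure |
|---|---|---|---|
| 2 | 18/20 = 90.0% | 16/18 = 88.9% | 16/20 = 80.0% |
| 4 | 18/20 = 90.0% | 14/16 = 87.5% | 14/20 = 70.0% |
| 6 | 18/20 = 90.0% | 12/14 = 85.7% | 12/20 = 60.0% |

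**No events.** N = 20, e = 0, d = 6: crude 20/20 and assessed-only 14/14 are both 100%. As a measure of information only (the SAP plans no intervals), the exact 95% lower limit is 0.025^(1/20) = 83.2% on 20 subjects and 0.025^(1/14) = 76.8% on 14.

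**Expected bias.** Assume one-year event risk p, constant hazard λ = −ln(1 − p), and a fraction f lost uniformly over the year for reasons unrelated to the device. The expected crude event proportion is (1 − f)p + f(1 − p/λ). For p = f = 0.20, λ = 0.223 and the result is 0.160 + 0.2 × 0.104 = 0.181, so the crude rate averages 81.9% against a true 80.0%. Over p and f from 10% to 30%, the upward bias runs from 0.5 points (90.5% against 90.0%) to about 4 points (74.2% against 70.0%).

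**If the losses are deaths.** Suppose the three losses in Example 1 are deaths, treated as a competing event. The cumulative incidence of device events is (8/10)(1/8) + (6/10)(1/6) = 0.1 + 0.1 = 0.2, whose complement, 80%, equals the crude rate. The crude count therefore does not overstate on that estimand when death is the only loss. The overstatement comes from withdrawal, loss and missing imaging.

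**The case against.** The strongest reply is that this is an unwritten denominator and not a wrong rule. A reader might infer that the SAP directs subjects without 12-month status to be counted as successes. It does not: no section sets the denominator for device integrity. SAP 5.1 is a general inclusion statement, and SAP 5.4.2 uses a smaller denominator alongside it. SAP 5.3 cannot be an exhaustive list of methods, since SAP 2.3.2 plans Kaplan-Meier for patency. A programmer could take assessed subjects only from SAP 5.2 or 5.4.2. All of this stands, and is why the point is put as the literal reading.

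It is also true that SAP 5.4.2 reports patency and component separation over imaged subjects, and that patency has a censored analysis, so much of the substance will appear elsewhere in the report. That softens the consequence. It does not settle the CEC-adjudicated composite, which is built from reported adverse events.

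A reader might further infer that the crude count always favours the device. It does not: the point estimates agree when there are no events, and crude equals Kaplan-Meier when every loss follows the last event. Nor is death ordinary loss; as a competing event it leaves the crude count defensible, and censoring it targets a setting in which nobody dies.

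Finally, the protocol's Appendix A, which holds the device-integrity definitions, and parts of the SAP were not available. Either could contain a follow-up requirement.

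**Conclusion.** The point holds as a consequence of reading SAP 2.3.2, 5.1 and 5.3 together. The one-year rate they produce does not move with the number of subjects lost, and credits withdrawn, lost and unimaged subjects without a reported event as event-free for the year. The crude rate is never below the Kaplan-Meier or assessed-only rate, and it is above Kaplan-Meier when at-risk subjects leave before a later event.

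The size depends on event and loss patterns that the documents do not give: about 7 points against Kaplan-Meier in the deliberately heavy 10-subject example, 4.3 points against assessed-only in the 20-subject example with 6 unassessed, and 0.5 to 4 points on average under 10–30% risk and 10–30% unrelated loss. If loss is related to device failure, these figures do not bound it.

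The endpoint is secondary and descriptive, with no hypothesis test (SAP 2.4). The change should be made, but the study's primary result does not depend on it.

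**What to change.** In SAP 2.3.2 and 5.3:

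1. Estimate device integrity and its components at 1, 6 and 12 months by a time-to-event method, as already planned for patency. State the day at which each estimate is read, since Table 2 lets 12-month data fall anywhere from day 243 to day 546.
2. Censor living event-free subjects at the last imaging that assessed the device. This differs from the patency rule (last follow-up or contact), so the SAP should say so.
3. Treat death as a competing event and report cumulative incidence, or censor at death and state that limitation.
4. Beside the crude count, show the numbers at risk, died, withdrawn and not imaged at each time point.
5. Do not use subjects with an event or 12-month imaging as the sole denominator. It keeps early failures but drops early event-free losses, so it leans against the device (71% against 73% by Kaplan-Meier in Example 1).

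The cost is SAP wording, one extra table and possibly a slightly less favourable reported rate. The CT imaging needed is already scheduled.

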### 4.0 Study Data Collection

#### 4.1 Study Data Collection Intervals

At the time of hospital discharge, Subjects will undergo a physical exam, a blood draw for general clinical health including BUN / Creatinine concentration and an abdominal ultrasound (optional).

Following hospital discharge, Subjects will be asked to return for follow-up visits at one month, six months, and annually for five years post-treatment. At each of these follow-up visits, Subjects will undergo an evaluation for adverse events. Evaluation methods will include a physical examination, a blood draw for BUN / Creatinine concentration, per-imaging guidelines spiral CTA of the abdomen and pelvis, and abdominal ultrasound (optional). Magnetic Resonance Angiogram (MRA) may be used as a follow-up imaging modality if the Subject is contraindicated for the required CTA follow-up. Table 1 outlines the required procedures at each follow-up visit.

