#### 4.5 Core Laboratory

Analysis of pre-treatment and follow-up radiologic images will be conducted by an independent Core Lab. At a minimum, the assessment will include:

- patency of components
- presence of endoleaks and vessel rupture
- presence of wire fractures and component separation
- maximum aortic diameter

The Core Lab may use the study imaging to further refine measurement techniques that could be applied in future studies.

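### Patency censoring at last contact keeps subjects without evaluable imaging in the Kaplan-Meier risk set as patent

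*SAP*

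**What the plan says.** SAP 2.3.2 sets the method, "Patency will be assessed using Kaplan-Meier analysis", and the censoring rule, "Subjects not experiencing an event will be censored at time of last follow-up or contact". It defines primary patency as "Blood flow without occlusion maintained through the device after implant without an intervention"; the assisted primary and secondary definitions also rest on blood flow through the device. Each measure then has a sentence that dates its loss. For primary patency, a subject with a qualifying reintervention or bypass "will have lost primary patency at the earliest such reintervention". The other two measures are dated in the same way, by reintervention or bypass for assisted primary patency and by open bypass for secondary patency.

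SAP 4.5 lists "patency of components" in the minimum Core Lab reading of images. SAP 5.4.2 summarises Core Lab patency by analysis window, with a denominator equal to the "number of subjects with a CT imaging assessment in the given window which is read by the Core Lab". On the schedule, SAP 4.1 says "Subjects will be asked to return for follow-up visits at one month, six months, and annually for five years post-treatment". Table 1 puts a contrast CTA at each of these visits, and SAP 4.1 allows MRA where CTA is contraindicated.

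**The concern.** The censoring date says how long an event-free subject was observed to be patent. A visit or contact without an image does not show that blood is still flowing through each branch, so it does not support that credit. Suppose a subject is last imaged at 6 months and then only contacted at 12 months. The written rule counts that subject as patent for the whole interval.

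Two things are at stake. The number at risk under the curve is larger than the number whose patency was known. If another subject loses patency in that interval, the loss is divided by too large a risk set and the estimate is too high. The same report could also list a subject as not assessed for patency in the by-window table of SAP 5.4.2 while carrying that subject as patent in the curve. With 10 treated subjects (Protocol Summary) or at most 20 (SAP 2.2), a few such subjects can be visible in the result.

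**Working it through.** **No figure to reproduce.** The documents give no target patency rate, no sample-size derivation and no missed-imaging rate. Everything numerical below is an illustration on assumed data.

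**Inputs.**
- From the documents: N = 20 (SAP 2.2 maximum) or N = 10 (Protocol Summary), Kaplan-Meier, and the two candidate censoring dates.
- Assumed: d losses of patency, all dated day 365; m event-free subjects last imaged at day 180 and contacted without imaging at day 370; all other event-free subjects imaged at day 370.

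**Formula.** With one event time, S = 1 − d/n. Last-contact censoring gives n = N. Last-image censoring gives n = N − m. The difference is d/(N − m) − d/N = d·m / [N(N − m)]. This is zero when d = 0 and never negative. The Greenwood standard error is S·√(d / [n(n − d)]).

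**Results for N = 20.**

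| d | Last contact (n = 20) | m = 2 (n = 18) | m = 4 (n = 16) | m = 6 (n = 14) | m = 8 (n = 12) |
|---|---|---|---|---|---|
| 1 | 0.950 | 0.944 | 0.938 | 0.929 | 0.917 |
| 2 | 0.900 | 0.889 | 0.875 | 0.857 | 0.833 |
| 3 | 0.850 | 0.833 | 0.813 | 0.786 | 0.750 |

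The smallest gap is 1×2/(20×18) = 0.0056, about 0.6 percentage points. The largest is 3×8/(20×12) = 0.100, or 10 points. For d = 2 the standard error is 0.067 under last contact, against 0.083 (m = 4) and 0.108 (m = 8) under last image, so the written rule also overstates precision.

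**N = 10, d = 1.** Last contact gives 9/10 = 0.900. Last image gives 6/7 = 0.857 (m = 3) or 4/5 = 0.800 (m = 5).

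**Expected value.** If unimaged subjects lose patency with the same probability p as the others but none of it is detected, and f is the unimaged share, the last-contact estimate is expected to be 1 − p(1 − f). For an assumed p = 0.10 the true value is 0.90. The estimate would be 1 − 0.10×0.9 = 0.91 at f = 0.1 and 1 − 0.10×0.6 = 0.94 at f = 0.4.

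**What happens if only the censoring date is changed.** Assume 10 subjects, all imaged as patent at month 12, one reintervention at month 18, and an analysis before the 24-month scans. With the other nine contacted at month 18 or later, the written rule gives 9/10 = 90%. Censoring those nine at month 12 leaves one subject at risk at month 18, and the estimate falls to 0/1 = 0%. If three of the nine already have month-24 images, it is 3/4 = 75%. Imaging-based censoring therefore needs a companion rule on how far the curve may be read.

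**The case against.** The strongest reply is that the rule fits the events as they are dated. Every event sentence in SAP 2.3.2 ties loss of patency to a reintervention or bypass, and a contact can establish whether one took place. That no contact can establish patency is an inference from the definition and the Core Lab's role, not a sentence in the SAP. This much stands, and it exposes a linked gap: an occlusion seen on imaging but never treated has no event date under any of the three measures. It does not rescue the rule, because the endpoint is defined as blood flow, not as freedom from reintervention. The censoring date and the event date have to be settled together.

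The second reply is that imaging is due at every visit from one month, so a completed visit normally includes it, and the SAP 5.4.2 summaries already use imaged subjects only. Both points stand. They limit how often the problem arises, but nothing carries the SAP 5.4.2 denominator over to the curve.

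The third reply, that imaging-based censoring can bias serial analyses downward, is correct, as the month-18 example shows. SAP 5.2 plans repeated long-term analyses, so the situation is foreseeable. It is an argument for a complete fix, not for keeping the rule.

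A reader might also infer that subjects with poor renal function will be the ones to miss imaging. The documents do not show this: they allow MRA where CTA is contraindicated and give no rate for either.

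**Conclusion.** The point holds as a conditional one. The written rule credits contacted but unimaged subjects as patent. Compared with imaging-based censoring on the same events, it can only leave the estimate unchanged or raise it. It always overstates the number at risk while such subjects are carried, but it moves the estimate only when another subject has an event between their last image and last contact.

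The size is unknown. The 0.6 to 10 points for 20 subjects rest on an assumed 10% to 40% unimaged share and 1 to 3 losses. A reader might infer that all three patency estimates are biased upward by several points. The documents do not support that: with complete imaging, or with no loss in the affected interval, the two rules give the same estimate.

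Patency is a descriptive secondary endpoint and no hypothesis test is planned (SAP 2.4, 5.3), so no error rate or power is affected. In a study without tests, though, the descriptive estimates are the result, and the change is worth making. Appendix A of the protocol and a few parts of the SAP were not available for this review and could not be checked for a rule that changes this.

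**What to change.** Amend the patency text of SAP 2.3.2 in four linked parts:

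- **Censoring.** Censor event-free subjects at the last imaging study on which patency of the treated segments was evaluable. State which modalities count, including MRA.
- **Event date.** For primary and assisted primary patency, date loss at the earlier of the first imaging-documented occlusion and the qualifying reintervention or bypass. State how an untreated occlusion counts for secondary patency.
- **Reporting limit.** Report Kaplan-Meier estimates only through the latest visit for which imaging of available subjects is complete, with the number having evaluable imaging shown under the curve. In the month-18 example, the curve would be read to month 12 until the 24-month scans are in.
- **Sensitivity analysis.** Repeat the analysis with last-contact censoring. The gap between the two shows how far the result leans on time without images.

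The cost is a short SAP revision using imaging dates and Core Lab reads already planned; a flag for evaluable patency must be derived if the reads do not carry one. The downside is shorter credited follow-up and somewhat lower, less precise late estimates. Changing the censoring date without the other parts is not advisable.
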